11.1 DATA AND SAFETY MONITORING PLAN	22
11.2 DATA MANAGEMENT PLAN	22

[figure not shown]
12 STATISTICAL CONSIDERATIONS	22
12.1 STATISTICAL DESIGN.....	22
12.2 OUTCOME MEASUREMENTS:	23
12.3 ANALYSIS PLAN:.....	23
12.4 SAMPLE SIZE	24
12.5 SAMPLE SIZE JUSTIFICATION.....	24
13 REFERENCES.....	24
14 APPENDICES	26
14.1 APPENDIX A: PARTICIPANT ELIGIBILITY CHECKLIST	26
15 SUPPORTING DOCUMENTATION*	27
14.2 APPENDIX B	28
14.3 APPENDIX C	29

PROTOCOL SYNOPSIS

TITLE	Feasibility of 3D perfusion ultrasound for liver cancer SABR planning and response evaluation
STUDY PHASE	Pilot
INDICATION	Evaluation of primary and/or metastatic liver tumor perfusion characteristics before and after Stereotactic Ablative Radiotherapy (SABR).
INVESTIGATIONAL AGENTS	Definity® Contrast Agent (perflutren lipid microspheres) for Ultrasound of the Liver.
PRIMARY OBJECTIVE(S)	The primary objectives of this pilot study is to (1) determine the feasibility and reproducibility of 3D contrast enhanced ultrasound imaging in liver patients undergoing Stereotactic Ablative Radiotherapy and (2) evaluate whether there are treatment induced early changes in imaging metrics derived from 3D contrast enhanced ultrasound. This study will provide valuable insight as to the potential of baseline and/or early post-treatment 3D ultrasound perfusion characteristics (measurements of blood-flow) of primary and metastatic liver tumors to predict tumor response to treatment.
TREATMENT SUMMARY	The study does not modify existing standard of care treatment. It only adds baseline and early contrast-enhanced ultrasound imaging with the DEFINITY® ultrasound contrast agent. DEFINITY® Vial (Perflutren Lipid Microsphere) for Injectable Suspension is Lantheus Medical Imaging Inc.'s non-blood based ultrasound contrast agent approved by the United States Food and Drug Administration (FDA). DEFINITY® is the first approved ultrasound contrast agent in the U.S. that offers flexible dosing and administration through IV bolus injection and continuous IV infusion.
SAMPLE SIZE	20
STATISTICAL CONSIDERATIONS	

SCHEMA

The following 3D Definity-enhanced ultrasound procedure will be performed at three patient visits: once prior to radiotherapy after the simulation CT scan, once at 0-7 days after the first fraction of radiotherapy treatment, and once in 2-4 months following the start of radiotherapy.

LIST OF ABBREVIATIONS AND DEFINITION OF TERMS

AE	Adverse event
BID	Twice daily
CBC	Complete blood count
CI	Confidence interval
CRF	Case report/Record form
CR	Complete response
CT	Computed Tomography
DCE	Dynamic Contrast Enhanced
DSMC	Data Safety Monitoring Committee
ECG	Electrocardiogram
FDA	Federal Drug Administration
ECOG	Eastern Cooperative Group Performance Status
GI	Gastrointestinal
Hgb	Hemoglobin
HTN	Hypertensions
IND	Investigational New Drug application
IRB	Institutional Review Board
IV	Intravenous
LLN	Lower limit of normal
MR	Magnetic Resonance
OS	Overall survival
PLT	Platelet
PD	Progressive diseased
PFS	Progression free survival
PR	Partial response
QD	Once daily
RCC	Renal Cell Carcinoma
RECIST	Response evaluation criteria in solid tumors
RR	Response rate
SAE	Serious adverse event
SD	Stable disease
SOP	Standard Operating Procedure
TTP	Time to progression
ULN	Upper limit of normal
UNK	Unknown
US	Ultrasonography, Ultrasound
WBC	White blood cell
3D	Three Dimensional
4D	Four Dimensional

1 OBJECTIVES

1.1 Primary Objective

The primary objectives of this prospective pilot study is to (1) determine the feasibility and reproducibility of 3D contrast enhanced ultrasound imaging in liver cancer patients undergoing Stereotactic Ablative Radiotherapy and (2) evaluate whether there are treatment induced early changes in imaging metrics derived from 3D contrast enhanced ultrasound. This study will provide valuable insight as to the potential of baseline and/or early post-treatment 3D ultrasound perfusion characteristics (measurements of blood-flow) of primary and metastatic liver tumors to predict tumor response to Stereotactic Ablative Radiotherapy. Our underlying goal is to assess whether early perfusion changes at 0-7 days after SABR initiation can be used as a non-invasive early biomarker for treatment response assessment.

1.2 Secondary Objectives

Evaluate the feasibility of contrast-enhanced ultrasound-to-CT fusion by assisting three-dimensional (3D) perfusion ultrasound (US) imaging with optical and electromagnetic tracking of the ultrasound probe on patients with liver cancer that will undergo CT for treatment planning and/or response evaluation.

2 BACKGROUND

2.1 Study Disease

Vascular damage and response have been implicated in the response to radiotherapy at ablative doses. Perfusion MR, CT, SPECT, and PET can be used to detect therapy-induced changes in tumor vascularity. However, radiation exposure from multiple exams (CT/PET/SPECT), restrictions on the use of contrast in patients with renal insufficiency (MR/CT), limited access (MR/SPECT/PET), and elevated cost render these modalities less practical for frequent routine imaging. Two-dimensional (2D) contrast-enhanced perfusion ultrasound (US) of injected microbubbles, is non-ionizing, accessible, and relatively inexpensive but fundamentally limited in quantification by the three-dimensional (3D) heterogeneity of tumor perfusion and the 3D nature of tumor motion.

These fundamental limitations of 2D US imaging have been recently overcome by the development of novel real-time 3D US transducers that make 3D dynamic US perfusion imaging in patients possible. Our goal is to assess the utility of 3D US perfusion for liver SABR planning and response evaluation.

2.2 Study Agent/Device/Procedure

DEFINITY® is comprised of lipid-coated microspheres filled with octafluoropropane gas. DEFNITY® does not contain any human or animal materials. The microspheres contained in DEFINITY® have a mean diameter of 1.1 to 3.3 microns (in vitro measurements). The

microspheres are stable and small enough to pass through the pulmonary capillaries. The microbubbles are eliminated via the breath.

For cardiac application, after activation of DEFINITY® and intravenous injection, the physical acoustic properties of activated DEFINITY® provide contrast enhancement of the endocardial borders during echocardiography. The perflutren lipid microspheres exhibit lower acoustic impedance than blood and enhance the intrinsic backscatter of blood (21).

In this study it is hoped that perfusion characteristics of the lesion will predict whether a patient will respond to therapy.

For clinicaltrials.gov compliance

This is an FDA approved drug for use in patients with suboptimal echocardiograms to opacify the left ventricular chamber and to improve the delineation of the left ventricular endocardial border.

This investigation is proposed to be conducted under IND exemption per 21CFR§312.2(b) and IRB approval.

2.3 Rationale

Medical imaging plays a prominent role in the clinical evaluation of cancer therapies. The Response Evaluation Criteria in Solid Tumors (RECIST) to evaluate anatomic response to treatment were developed to standardize tumor measurements in routine clinical care and in clinical trials (1). With the use of RECIST, patients are classified to either respond, stabilize, or progress, depending on treatment-induced changes in tumor size measured on computed tomographic (CT) scans or magnetic resonance (MR) images. However, cancers treated with the new generation of targeted therapies (e.g., such as anti-angiogenic agents) often show little change in size during the 1st months of therapy despite substantial clinical benefit. Radiologic criteria that additionally take into account functional changes in the enhancement of lesions on contrast material-enhanced CT scans (3,4) or dynamic contrast-enhanced (DCE) MR images (5) have helped to identify patients who went on to show clinical benefit as early as 9 weeks into treatment (6).

DCE ultrasonography (US) can be used to quantify microbubble enhancement and can be used to assess functional change in response to antiangiogenic treatment of patients with metastatic RCC. The advantage of DCE US are the lack of ionizing radiation (as compared to CT) and the relatively low costs and availability (compared to MRI). Furthermore, US contrast agents are not nephrotoxic and, therefore, can be injected with renal insufficiency. Recent research showed feasibility of two-dimensional (2D) DCE US in patients. Lamuraglia et al (7) described DCE US criteria to classify the response to sorafenib (Nexavar; Bayer, West Haven, Conn). Correlations between changes in DCE US parameters, during the first 2 weeks of treatment with sorafenib, and overall survival have also been reported (8), while revascularization of tumors following the cessation of treatment with bevacizumab (Avastin; Hoffmann-La Roche, Basel, Switzerland) has been characterized by using a DCE US-derived perfusion index, which correlates with histologic findings in a murine tumor model (9). Other preclinical studies of antiangiogenic treatments have demonstrated correlations between DCE US and DC CT measurements (10) and among DCE US, DCE MR

imaging, and fluorine 18 fluorodeoxyglucose positron emission tomographic measurements (11).

Dynamic contrast-enhanced ultrasonography (DCE-US) is a technique that can be used to detect microvessels and quantitatively assess solid tumor perfusion using raw linear data (15). It involves Doppler ultrasound after injection with a contrast agent, which enhances the vessel signal (16, 17). Doppler ultrasonography can accurately detect and characterize blood flow in vessels with a diameter as low as 100 μm (14). Doppler signals provide functional information on neovascularity by indicating the maximal velocity in tumor supply vessels (16). The addition of perfusion software and microbubble contrast agents has further improved the technique, enabling the visualization of vessels with a diameter as small as 40 μm (17). To date, DCE-US has been used in a number of clinical trials with receptor tyrosine kinase inhibitors. These studies have indicated that DCE-US parameters may be correlated with tumor responses, for example in RCC with sorafenib (18, 19) or in gastrointestinal stromal tumors (GIST) treated by imatinib (20).

Dynamic US can be used to quantify dynamic changes in tumor vascularity as early as 3 days after bevacizumab administration in patients with HCC. These early changes in tumor perfusion may be predictive of tumor response at 2 months, progression-free survival, and overall survival, and they may be potential surrogate measures of the effectiveness of antiangiogenic therapy in patients with HCC (13).

However, a major limitation of current perfusion US studies is that all imaging is performed in a limited two-dimensional (2D) field-of-view which cannot capture the heterogeneity of tumor perfusion throughout its volume. Recent animal studies have shown that a 2D sampling of tumor perfusion may be highly biased by the position of the US transducer placement over the tumor and that entire-tumor three-dimensional (3D) imaging approaches are of paramount importance to translate non-invasive perfusion US into a clinical applications (12).

Through our research collaboration with Philips, we have acquired a new FDA approved 3D US transducer that allows 3D DCE-US perfusion imaging of an extended field-of-view. This allows for the first time to quantify tumor perfusion of the entire volumetric extent of a liver metastasis and will likely substantially improve reliability and accuracy of US perfusion imaging in the clinical arena.

In this pilot study, we will assess performance of 3D US perfusion imaging in patients with liver tumors undergoing SABR to evaluate the feasibility of performing 3D perfusion CEUS in this patient population and understand whether early changes in perfusion parameters are introduced as a result of the SABR treatment.

2.4 Study Design

For clinicaltrials.gov and Stanford Clinical Trials Directory compliance

This is a pilot, single-center study in subjects with liver tumors. The primary objectives of this prospective pilot study is to (1) determine the feasibility and reproducibility of 3D contrast

enhanced ultrasound imaging in liver cancer patients undergoing Stereotactic Ablative Radiotherapy and (2) evaluate whether there are treatment induced early changes in imaging metrics derived from 3D contrast enhanced ultrasound. This study will provide valuable insight as to the potential of baseline and/or early post-treatment 3D ultrasound perfusion characteristics (measurements of blood-flow) of primary and metastatic liver tumors to predict tumor response to Stereotactic Ablative Radiotherapy.

The target lesion will be located at the simulation CT scan for treatment planning. Prior to Definity® administration, gray scale and Doppler (color or power imaging) ultrasound investigations of the target lesion will be performed using commercially available ultrasound equipment and standard techniques (B-mode or Harmonic imaging) to study the anatomy of the target lesion and surrounding parenchyma.

Immediately after the unenhanced ultrasound evaluation, contrast-enhanced ultrasound will be performed, according to the procedures described to study the lesion vascularity in comparison to the surrounding parenchyma. Definity® will be administered intravenously through a central line or in a peripheral vein.

Unenhanced ultrasound and Definity®-enhanced ultrasound images will be recorded and stored anonymously.

The primary analysis will be based on comparison of the readout (perfusion parameters of the lesion) at baseline, at 0-7 days after the first fraction of radiotherapy treatment, 2-4 months following the start of radiotherapy, and the clinical outcome of the patient, including findings on routine CT and PET-CT imaging.

This is a Single Group, Open Label Study designed to evaluate to evaluate as a primary outcome feasibility and efficacy.

2.5 Correlative Studies Background

Correlative studies background is not provided, as there are no correlative studies planned.

3 PARTICIPANT SELECTION AND ENROLLMENT PROCEDURES

All patients consulted for Stereotactic Ablative Radiotherapy (SABR) treatment of primary or metastatic liver tumors will be considered for this study.

3.1 Inclusion Criteria

3.1.1 Ability to understand and willingness to sign the written informed consent document

3.1.2 Patient with primary liver tumor or metastasis scheduled for Stereotactic Ablative Radiotherapy (SABR)

3.1.3 Patient is at least 18 years of age. No gender/race-ethnic restrictions.

3.1.4 Performance status (ECOG) between 0-3

3.1.5 History and Physical done within 4 weeks of enrollment.

3.2 Exclusion Criteria

3.2.1 Patient has previously been enrolled in and completed this study.

3.2.2 Known right to left cardiac shunt, bidirectional or transient.

3.2.3 Patient has any medical condition or other circumstances which would significantly decrease the chances of obtaining reliable data, achieving study objectives, or completing the study and/or post-dose follow-up examinations.

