4.2 Criteria for Removal from Study

Subject will be discontinued from the study if the subject:

- withdraws consent.
- during the course of the study manifests condition matching exclusion criteria.
- will not be able to adhere to protocol timeline due to scheduling or other conflict
- has an adverse event that, in the opinion of the Investigator, requires the subject's Discontinuation.

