DEFINITY® is not to be administered in patients with known or suspected right-to-left, bi-directional or transient right-to-left cardiac shunts, by intra-arterial injection, or to patients with known hypersensitivity to perflutren. In post marketing use, rare but serious cardiopulmonary or anaphylactoid reactions have been reported during or shortly following perflutren-containing microsphere administration. The risk for these reactions may be increased among patients with unstable cardiopulmonary conditions. It is not always possible to reliably establish a causal relationship to drug exposure due to the presence of underlying cardiopulmonary disease. Thus all patients need to be assessed for the presence of any condition that precludes DEFINITY® administration and it is recommended that resuscitation equipment and trained personnel are readily available.

Devices:

In addition, there will be an Optical and Electromagnetic tracking tools attached to the Ultrasound Transducer that will not be in contact with the patient. There is very little risk to the patient associated with optical tracking as there is no transfer of energy to the patient. With electromagnetic tracking there may be electromagnetic interference with implantable devices such as pacemakers, etc. Electromagnetic tracking will not be used (Optical tracking only) if the patient has an implantable medical device to eliminate risk from electromagnetic interference.

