14 APPENDICES

14.1 APPENDIX A: Participant Eligibility Checklist

I. Protocol Information

Protocol Title:	Feasibility of 3D perfusion ultrasound of liver cancer SABR planning and response evaluation
Protocol Number:	IRB-30071 / HEP0048
Principal Investigator:	[name]

II. Subject Information:

Subject Name/ID:
Gender:  Male  Female

III. Inclusion/Exclusion Criteria

Inclusion Criteria	Yes	No	15 Supporting Documentation*
1. Ability to understand and willingness to sign the written informed consent document.			
2. Patient with primary liver tumor or metastasis scheduled for Stereotactic Ablative Radiotherapy (SABR)			
3. Patient is at least 18 years of age. No gender/race-ethnic restrictions.			
4. Performance status (ECOG) between 0-3			
5. History and Physical done within 4 weeks of enrollment.			
Exclusion Criteria			
1. Patient has previously been enrolled in and completed this study.			
2. Known right to left cardiac shunt, bidirectional or transient.			
3. Patient has any medical condition or other circumstances which would significantly decrease the chances of obtaining reliable data, achieving study objectives, or completing the study and/or post-dose follow-up examinations.			

4. History of hypersensitivity perflutren			
5. History of pulmonary hypertension			
6. Patients who are pregnant or are trying to become pregnant			

*All subject files must include supporting documentation to confirm subject eligibility. The method of confirmation can include, but is not limited to, laboratory test results, radiology test results, subject self-report, and medical record review.

IV. Statement of Eligibility

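### The cardiac-shunt exclusion and its checklist item cover only known shunts, while the contraindication in section 5.1 also covers suspected ones; the three texts must be reconciled

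*Combined protocol and SAP*

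**What the plan says.** Three places in the combined protocol and SAP deal with cardiac shunts.

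- Section 3.2, exclusion 3.2.2: "Known right to left cardiac shunt, bidirectional or transient".
- Appendix A (Participant Eligibility Checklist), exclusion item 2: "2. Known right to left cardiac shunt, bidirectional or transient".
- Section 5.1, under the contraindications: "DEFINITY® is not to be administered in patients with known or suspected right-to-left, bi-directional or transient right-to-left cardiac shunts".

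Three other provisions bear on how a suspected shunt would be handled.

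- Section 5.1 goes on to say that "all patients need to be assessed for the presence of any condition that precludes DEFINITY® administration".
- Exclusion 3.2.3, repeated as Appendix A item 3, is a general clause. It covers conditions or circumstances that would make reliable data less likely, or would reduce the chances of "achieving study objectives, or completing the study and/or post-dose follow-up examinations".
- Section 4.2 removes a subject who "during the course of the study manifests condition matching exclusion criteria".

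On exposure, the Schema states: "The following 3D Definity-enhanced ultrasound procedure will be performed at three patient visits". Section 12.4 sets the sample size at 20 patients.

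**The concern.** The eligibility criterion and checklist line written for this contraindication are narrower than the contraindication. A screener can answer the shunt line truthfully for a patient whose shunt is only suspected, record no exclusion, and leave the condition in section 5.1 unaddressed. Whether that patient is identified at screening then depends on staff recalling 5.1 or using their judgement under 3.2.3.

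What is at stake is patient safety: a patient whom the protocol says must not receive the agent could be enrolled, with the agent planned at every imaging visit. Nothing statistical is at stake. Estimation of the concordance correlation, the summaries of relative change and the feasibility proportions do not depend on this wording.

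**Working it through.** No figure in the plan is in dispute, so the check is a comparison of texts followed by a simple count.

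**1. The shunt texts side by side**

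| Place | Function | Known shunt | Suspected shunt |
|---|---|---|---|
| 3.2.2 | Exclusion criterion | Covered | Not covered |
| Appendix A, exclusion item 2 | Checklist line | Covered | Not covered |
| 5.1, contraindications | Bar on giving the agent | Covered | Covered |

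The two eligibility texts agree with each other. The mismatch is between that pair and 5.1. All three name the same shunt types and differ only in the degree of certainty required.

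**2. Whether the exclusion list is meant to carry the contraindications**

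Section 5.1 names two patient-level contraindications, shunt and hypersensitivity to perflutren. Each has its own exclusion item (3.2.2 and 3.2.4). The hypersensitivity item turns on a history of the reaction and is at least as broad as its counterpart in 5.1. Only the shunt item is narrower, and the documents give no reason for the difference.

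**3. Whether another provision names a suspected shunt**

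- Of the other exclusions, 3.2.1 and 3.2.4 to 3.2.6 concern previous participation, hypersensitivity, pulmonary hypertension and pregnancy. None covers a suspected shunt.
- Exclusion 3.2.3 names neither shunts nor contraindications. It reaches this patient by inference: the agent may not be given, so the contrast examinations cannot be completed. The inference starts from knowing the bar in 5.1.
- The study calendar (section 9) lists history and physical, eligibility, performance status and a pregnancy test at enrollment. It has no separate line for contraindications to the agent.
- The removal rule in 4.2 refers to the exclusion criteria as a whole. For a shunt first suspected after enrollment, it depends on the same judgement under 3.2.3. The bar in 5.1 still applies to any further administration.

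**4. Whether the texts can be followed together**

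Yes. Exclusion 3.2.2 is silent on suspected shunts and does not permit administration, and 5.1 forbids it. This is a difference in breadth. No text orders what another forbids.

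**5. Count**

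- Inputs: 20 patients (section 12.4) and 3 visits with the agent (Schema).
- Planned examinations governed by the screening items: 20 × 3 = 60.
- Per patient: 60 / 20 = 3. A patient with a suspected shunt who was caught by neither 5.1 nor 3.2.3 would have up to 3 planned administrations.

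The documents give no rate of suspected shunt, so the 60 cannot be turned into an expected number of affected patients.

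**The case against.** The strongest reply is that nothing here is a contradiction and that the protocol already protects the patient. Section 5.1 forbids administration outright and places a duty of assessment on staff for every patient. To say that detection depends on recalling 5.1 is to suppose that staff do not follow the protocol. Every perfusion measure comes from the contrast infusion, so a patient barred from the agent can yield none of them, and 3.2.3, which is also on the checklist, then plainly applies. A history and physical within 4 weeks of enrollment gives a clinical contact at which the assessment can be made. Three safeguards would have to fail before exposure occurred: the bar, the assessment duty and 3.2.3. The size of the problem is unknown, and 60 examinations do not measure it. On this view the point is minor drafting.

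Much of this stands. The texts can be followed together, the protocol does not direct exposure, and the consequence cannot be quantified. Two things remain. First, 3.2.3 works only after someone has recognised the bar in 5.1, so it is not an independent safeguard. The documents also do not say that the history and physical includes assessment for a shunt. Second, the checklist already has a line for this very condition, and Appendix A requires each subject file to contain documents confirming eligibility. The wording of that line therefore shapes what is verified and recorded. The general provisions do not make it match the contraindication.

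**Conclusion.** The point holds. Exclusion 3.2.2 and Appendix A item 2 are narrower than the contraindication in section 5.1, and a patient with a suspected shunt passes the item written for that condition. It should be fixed but is not critical, because 5.1 already bars administration.

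Confidence is high for the difference in wording. The practical consequence is uncertain: it depends on how staff apply 5.1 and 3.2.3, and the number of patients concerned cannot be estimated from the documents. The most that can be said is that a patient missed by both would have up to 3 planned administrations. The sample size and the analysis are unaffected.

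The conclusion rests on the exclusion items as they appear in Appendix A. The eligibility sign-off that follows them was not available for review and might contain a further check.

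**What to change.** Reconcile exclusion 3.2.2, Appendix A exclusion item 2 and the contraindication text in section 5.1 so that all three carry the same wording on shunts. The sponsor's clinicians should decide what that wording is; this review takes no position on it. Section 4.2 needs no edit, because it refers to the exclusion criteria and will follow whatever they say.

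The cost is an alignment of wording across one criterion, one checklist line and the contraindication text. It needs no additional patients, visits or statistical work.
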